5.11 Infection Prophylaxis and Monitoring

Pneumocystis jiroveci prophylaxis: Aerosolized pentamidine will be used as prophylaxis against *Pneumocystis jiroveci*, 300 mg approximately every 4 weeks by inhalation beginning the first month of therapy and to continue for 6 months total for subjects 5 years of age and older for all cohorts. Dapsone or another prophylactic regimen against *Pneumocystis jiroveci* may be substituted at the discretion of the PI. Bactrim (TMP/SULF) will be avoided because trimethoprim is a moderate to strong inhibitor of CYPs that may theoretically result in enhanced activity of eltrombopag. Children under 5 years of age (approximate) are often not able to complete the inhalation treatment with pentamidine and will receive dapsone or another prophylactic regimen at the discretion of the PI.

Antiviral prophylaxis: Valacyclovir, 500 mg once daily, will be administered for at least 1 month in all subjects regardless of HSV serology status. Pediatric subjects less than 40 kg, will receive acyclovir (or equivalent) at 20mg/kg PO q12h to a maximum dose of 800mg q12h. Prophylaxis may be extended at the discretion of the PI.

Antibacterial and antifungal prophylaxis will not be included systematically with the

immunosuppressive regimen, but may be administered at the discretion of the PI or treating physician on a case-by-case basis.

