5.2 Cyclosporine (CsA)

Day 1 to Month 6 dosing:

For subjects \geq 12 years of age, cyclosporine will be started on day 1 at 3 mg/kg/dose by mouth administered every 12 hours (total daily dose of 6 mg/kg/day). Dosing will be based on actual body weight except in obese subjects. For obese subjects (defined as a body mass index > 35 in adult subjects [> 20 years of age] and > 95 th percentile in subjects 12 to 20 years of age), cyclosporine dosage will be based on an adjusted body weight that is calculated as the midpoint between the ideal body weight and actual body weight (see below for definition of ideal body weight).

For subjects $<$ 12 years of age, cyclosporine will be started on day 1 at 6 mg/kg/dose by mouth administered every 12 hours (total daily dose of 12 mg/kg/day). Dosing will be based on actual body weight except in obese subjects. For obese subjects (defined as a body mass index > 95 th percentile in subjects 12 to 20 years of age), cyclosporine dosage will be based on an adjusted body weight that is calculated as the midpoint between the ideal body weight and actual body weight (see below for definition of ideal body weight).

Cyclosporine dosing will be adjusted, at the investigator's discretion, to aim for a therapeutic trough level between 200 and 400 mcg/L. In subjects who had a therapeutic CsA level established prior to protocol enrollment, the same CsA dose will be initiated with the h-ATG and adjusted accordingly. Cyclosporine dose may be interrupted or adjusted as clinically indicated at the discretion of the investigator for side effects. Interruptions will only be recorded in the medical record.

In between NIH landmark visits, only CsA levels will be tracked and recorded into the clinical database.

Ideal Body Weight Definitions:

Ideal body weight (adult male, age > 20): 50 kg + 2.3 kg per inch over 5 feet

Ideal body weight (adult female, age > 20): 45.5 kg + 2.3 kg per inch over 5 feet

Ideal body weight (pediatrics, ages 2–20): 50th percentile weight based on CDC growth curves.

Month 6 to Month 24 cyclosporine dosing:

On review of the data as of September 17, 2014 where a trend towards a higher than expected number of relapses after the 6 month landmark visit were observed and salvaged by resuming cyclosporine, the protocol was amended to prolong administration of cyclosporine beyond 6 months per the following:

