At the 6-month landmark visit, responders will have the CsA dose reduced to 2.0mg/kg/day administered orally at a fixed dose through the 24 month timepoint. Previous anecdotal experience suggested that a gradual taper of CsA may avoid relapse, but when we adopted this strategy prospectively in our clinical trials (03-H-0193 and 06-H-0034) the rate of relapse was unchanged (Scheinberg, Rios, et al. AJH 2014⁶⁷). However, time to relapse was delayed by 1 year with the longer course of CsA and may be dose-dependent. The CsA dose at the time of relapse during the taper phase was at a median of 1.32 (range: 0.52-4.18) mg/kg/day and a mean of 1.8 mg/kg/day. This suggests that a CsA dose level above these levels might preclude relapse and improve tolerability of chronic maintenance. For remaining subjects due for the 6 month timepoint on cohort 2 we will prolong administration of cyclosporine beyond 6 months. CsA will continue to be administered from Day 1 to 6 months, but from 6 months to 2 years CsA will be administered at a lower fixed daily dose (2 mg/kg/day) in an attempt to improve relapse, a secondary endpoint, among responders in the study.

Medication dosing errors, dose delays or dosing interruptions:

Interruptions such as delays in request for medication refills or medication errors by subjects will be recorded in the medical record.

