5.7 Extended Access to Study Drug

Responders:

Cohorts 1 and 2: Study drug (eltrombopag) administration will be discontinued at 6 months for subjects in cohort 1 and at 3 months* for subjects in cohort 2; cyclosporine will be discontinued at 6 months for both cohorts.

Cohorts 1 and 2 Subjects that Relapse:

In cohort 2, if a subject who received eltrombopag for 3 months* has evidence of relapse as defined in Section 7, eltrombopag and/or cyclosporine can be restarted at the clinical investigator's discretion. Such cohort 2 subjects, who require treatment prior to month 6, will be denoted as non-responders at 6 months

for statistical purposes.

Subjects in cohort 1 or 2 that relapse (defined in section 7) after the end of 6-month treatment period while in follow-up may have eltrombopag and/or cyclosporine restarted at the clinical investigator's discretion. Subjects in cohort 2 that received the reduced CsA dose (2mg/kg/day) starting after the 6-month landmark visit who relapse despite the prolonged reduced dose of CsA may have the CsA dose increased to achieve therapeutic levels (trough levels 200-400) at the clinical investigator's discretion. Subjects can remain on the drugs under this protocol until the end of the 5 year follow-up period.

*Study drug (eltrombopag) administration will be discontinued at 3 months for subjects in cohort 2, except for subjects experiencing dose delays/interruptions as outlined in Section 5.3.

Cohort 3 and Extension Cohort:

Subjects that relapse (defined in section 7) after the end of 6-month treatment period while in follow-up may have eltrombopag restarted at the clinical investigator's discretion. In addition, the cyclosporine dose may be increased to achieve a therapeutic level. Subjects can remain on the drugs under this protocol until the end of the 5-year follow-up period.

Laboratory Exploratory Cohort:

Follow up for subjects in this cohort will be the same as Cohort 3 and Extension Cohort (above).

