Inhibitors of cytochrome p450: In vitro studies demonstrate that CYP1A2 and CYP2C8 are involved in the oxidative metabolism of eltrombopag. Trimethoprim, gemfibrozil, ciprofloxacin, fluvoxamine and other moderate or strong inhibitors of CYPs may therefore theoretically result enhanced activity of eltrombopag, however these interactions have not yet been established in clinical studies. All subjects on cyclosporine require prophylaxis against PCP and will be given inhaled pentamidine instead of TMP/SULF. NIH SAA patients are routinely placed on pentamidine instead of TMP/SULF for PCP prophylaxis to avoid potential marrow-suppressive effects of TMP/SULF anyway. Subjects aged 5 years and over will receive pentamidine for PCP prophylaxis but children under 5 years of age (approximate) are often not able to complete the inhalation treatment with pentamidine and will receive dapsone or another prophylactic regimen. Other CYP inhibitors can be used concomitantly but with careful attention to possible increased eltrombopag activity and toxicity.

Other medications: Subjects may continue on any of the medications that they were prescribed prior to study enrollment for co-morbid conditions, with the exception of N-Plate and Neumega (see 5.9).

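### Sections 5.10 and 5.11 give conflicting rules on PCP prophylaxis once cyclosporine continues past month 6 or is restarted or raised for relapse

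*Combined protocol and SAP*

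**What the plan says.** **Who needs prophylaxis.** Section 5.10, in the paragraph on cytochrome P450 inhibitors, states: "All subjects on cyclosporine require prophylaxis against PCP and will be given inhaled pentamidine instead of TMP/SULF". It names no CsA dose, period or cohort. Subjects aged 5 and over are to have pentamidine. Those under about 5 are to have dapsone or another regimen.

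**How long it lasts.** Section 5.11 starts pentamidine in the first month of therapy, "and to continue for 6 months total for subjects 5 years of age and older for all cohorts". For younger children it gives a choice of agent but no duration. On the PCP agent, another regimen "may be substituted at the discretion of the PI". A separate paragraph on antivirals adds: "Prophylaxis may be extended at the discretion of the PI".

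**How long CsA lasts.** Section 5.2 records that "the protocol was amended to prolong administration of cyclosporine beyond 6 months per the following", and then that at the 6-month visit "responders will have the CsA dose reduced to 2.0mg/kg/day administered orally at a fixed dose through the 24 month timepoint". Secondary endpoint (g) in section 9.4 describes the same 18-month low-dose phase.

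**What happens at relapse.** Section 5.7 allows CsA to be restarted in cohorts 1 and 2. Cohort 2 subjects who relapse on the reduced dose may have it raised to a trough of 200-400. For cohort 3 and the Extension Cohort: "In addition, the cyclosporine dose may be increased to achieve a therapeutic level". The Laboratory Exploratory Cohort follows the same rule. Drug may continue to the end of the 5-year follow-up.

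**The concern.** Someone caring for a subject on CsA after month 6 finds one section that requires prophylaxis for as long as CsA is taken and another that has already ended it. The same reader finds nothing on prophylaxis when CsA goes back to therapeutic levels for relapse. Sections 6.3 and 6.4 let home physicians carry much of the care after discharge, so the text has to be clear to people outside the study team.

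What is at stake is a safety instruction for immunosuppressed patients, children among them. Section 11.4.2 itself says that CsA adds to the infection risk that comes with low white cell counts.

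**Working it through.** The plan states no statistical figure on this point, so there is none to reproduce. The check sets the CsA schedule beside the prophylaxis rules.

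| Period | CsA under 5.2 and 5.7 | Rule in 5.10 | Rule in 5.11, age 5 and over | Rule in 5.11, under about 5 |
|---|---|---|---|---|
| Day 1 to month 6 | Full dose, trough 200-400 | Required | Pentamidine given | Other regimen, no end stated |
| Month 6 to 24, responders | 2 mg/kg/day | Required | Ended | No end stated |
| Re-treatment for relapse, to year 5 | Restarted, or raised to therapeutic levels | Required | Ended if after month 6; no restart stated | No end stated |

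**Length of the gap, age 5 and over**

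- Scheduled CsA ends at month 24 and a 6-month pentamidine course begun at the outset ends at month 6: 24 − 6 = 18 months. If pentamidine starts only at the end of the first month, its course ends at about month 7 and the gap is 24 − 7 = 17 months.
- With re-treatment, CsA may continue to year 5, which is month 60. The ceiling is 60 − 6 = 54 months, reached only by a subject who is on CsA throughout.

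**Who is on CsA after month 6**

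- Low-dose phase: responders among the cohort 2 subjects who had not reached their 6-month visit when section 5.2 was amended, in cohort 3, and in the Extension and Laboratory cohorts, which follow the cohort 3 schedule (section 3).
- Re-treatment: relapsing subjects in any cohort. Cohort 1 meets the conflict only by this route.

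**Does any other text close the gap?**

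- The discretion in the PCP paragraph of 5.11 covers the agent. The sentence allowing a longer course is in the antiviral paragraph.
- Section 6.5 lists what may be done when drugs are restarted, including bringing CsA levels back to 200-400 ng/ml. PCP prophylaxis is not mentioned.
- Section 11.4.2, on prolonged low-dose CsA, says that infections are few. It does not mention PCP, does not exempt anyone from 5.10, and concerns the 2 mg/kg/day dose.
- Section 5.7 still has CsA stopping at 6 months for cohorts 1 and 2, which does not match 5.2 for the later cohort 2 subjects. A reader relying on 5.7 might not see the conflict.

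**The case against.** The strongest reply is that the 6-month limit is intended. Section 5.11 is the dedicated prophylaxis section and alone gives dose, interval and duration. The sentence in 5.10 is mainly about why pentamidine replaces TMP/SULF, and it states no competing duration. The duration sentence in 5.11 refers to all cohorts, which suggests it was edited after cohorts were added. Section 6.3 likewise ends CsA level monitoring at 6 months for all cohorts, and section 11.4.2 treats low-dose CsA as carrying little infection risk. Together these make a deliberate limit for the low-dose phase plausible. That stands. But 5.10 is then too broad as written, since it makes no exception for low-dose CsA, and the reply does not reach re-treatment at therapeutic levels.

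A reader might infer more than the documents support:

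- *That 5.11 was overlooked when CsA was prolonged.* Its edit history is not shown, and the reference to all cohorts points, if anything, the other way.
- *That the 6-month limit also binds children under 5.* It is written only for those aged 5 and over. For younger children the defect is a missing duration.
- *That a known number of subjects is affected.* Cohort 3, Extension and Laboratory cohorts total 31 + 87 + 25 = 143. Assuming 60% response (the low end of the historical range in section 9.2) gives 143 × 0.60 ≈ 86, and assuming 84% (the early figure in section 2.9.1) gives 143 × 0.84 ≈ 120. That counts everyone who would ever enter the low-dose phase, including any under-5s. Without enrolment dates it does not show how many a change could still reach.
- *That uneven prophylaxis biases survival or relapse.* Infection could bear on both, since section 7 sets aside count declines explained by infection. But the documents give no PCP rate and no evidence that practice differed between physicians.

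**Conclusion.** The inconsistency is real. As written, 5.10 requires PCP prophylaxis for every subject on CsA, while 5.11 ends pentamidine after 6 months for those aged 5 and over. About 18 months of scheduled low-dose CsA for responders falls between the two rules. For re-treatment after relapse the protocol gives no explicit instruction, and that exposure can run to year 5. The conflict is clearest there, because nothing in the protocol offers a reason for leaving out prophylaxis at therapeutic CsA levels.

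The conclusion rests on reading 5.10 literally and on CsA being given as 5.2 and 5.7 describe. It says nothing about what was done in practice or which rule is clinically right. The primary endpoint is complete response at 6 months, within the stated prophylaxis period. The two-stage design, its power and the stopping boundaries are unaffected.

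**What to change.** Reconcile 5.10 and 5.11 with the CsA schedule in 5.2 and the relapse provisions in 5.7, so that one consistent statement covers:

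- low-dose CsA from month 6 to month 24;
- CsA restarted or raised to therapeutic levels for relapse, with a cross-reference in 6.5;
- both age groups, including a stated duration for children under about 5.

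If the 6-month limit is intended for the low-dose phase, say so in 5.11 and qualify 5.10 to match. If 5.10 is intended as written, align the duration in 5.11 with it. The sponsor decides which. The remaining statement in 5.7 on stopping CsA at 6 months should be brought into line with 5.2 in the same amendment.

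The cost is protocol wording and a notice to home physicians. Depending on the rule chosen, some subjects may have a longer course of a drug already in the protocol. No analysis or sample size changes.

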5.12 Management of Fever in Neutropenic Subjects (All subjects)

Subjects with a single temperature of 38.5 °C or two readings of 38.0 °C or greater will be evaluated for infection including cultures of blood and urine and any other suspicious sites prior to beginning empiric therapy. Antibiotics will be initiated following current infectious disease guidelines.

5.13 Instructions to Subjects

Special Instructions regarding CsA:

Regarding concomitant medications: Certain other medications can change the level of cyclosporine in the blood. Some of these medications are erythromycin, ketoconazole, diltiazem, rifampin, phenytoin and phenobarbital. We will ask subjects to inform us of any medication taking concomitantly while on the study.

Regarding prohibited foods: Grapefruit and grapefruit juice may increase the effects of CsA by increasing the amount of this medicine in the body. Subjects will be advised not to eat grapefruit or drink grapefruit juice while taking this medicine.

Regarding Immunizations: While taking CsA and for at least three months following discontinuation, immunizations should be avoided, and any planned immunization should be discussed with study investigators. There is almost no possibility that a vaccination given during this time period will be effective in stimulating immunity. Any live or attenuated vaccine may result in an infection, due to compromised immunity on CsA and h-ATG. Subjects should also avoid close household contact with individuals receiving the live oral polio vaccine for at least 72 hours following administration.

Special Instructions regarding eltrombopag:

Timing in relation to food: Subjects will be advised to take eltrombopag on an empty stomach (1 hour before or 2 hours after a meal), or adhere to a restricted diet of low calcium (dairy products) and polyvalent cations at least 4 hours apart from co-administration of eltrombopag.

Timing in relation to antacids and polyvalent cations: Because co-administration of eltrombopag with antacids decreased plasma AUC of eltrombopag by 70%, subjects will be advised to take the eltrombopag at least 4 hours apart from antacids and other products containing polyvalent cations (i.e. aluminum, calcium, magnesium, iron, selenium and zinc) such as mineral supplements and dairy products.

5.14 HRQL Questionnaires

The relevant dimensions of HRQL being assessed in this study include (1) PROMIS Global Health, Sleep Disturbance, Applied Cognition-Abilities, Anxiety and Depression and (2) FACT- Anemia, Thrombocytopenia and Neutropenia.

Patient-Reported Outcomes Measurement Information System (PROMIS®), is an initiative based on an NIH grant to establish and provide the public a free, reliable and validated commonly used measures of patient-reported outcomes.⁶³

The FACT instruments⁶⁴ are a health assessment instrument designed to measure multi-dimensional quality of life in chronic illness and its associated therapy. The different subscales selected for this study are

specific for patients with diseases or treatments with hematological effects. All measures will be offered to adult subjects who read English or Spanish. Any survey time-point that is missed due to the subject's clinical status (e.g. critically ill) will be reported as a protocol deviation at time of continuing review.

6. CLINICAL MONITORING

Samples will be ordered and tracked through the CRIS Screens. Should a CRIS screen not be available, the NIH form 2803-1 will be completed and will accompany the specimen and be filed in the medical record. HRQL surveys will be mailed to the subject if they are not required to return to the NIH CC for study evaluations.

6.1 Pre-study Evaluation - PI may accept results from studies done outside of NIH.

Baseline studies will be conducted as follows:

- Medical history and physical examination
- Concurrent medication review
- HRQL survey administration (Surveys will not be required for the Extension and Exploratory Laboratory Cohort)
- Baseline clinical studies
 - Complete blood count with differential
 - Reticulocyte count
 - DAT (direct antiglobulin test)
 - Type and screen
 - Acute Care (Na, K, Cl, CO₂, Creatinine, Glucose, and Urea Nitrogen), Mineral (Phosphorus, Magnesium, Albumin, and Calcium), Hepatic (Alk Phosphatase, ALT, AST, Total Bilirubin, and Direct Bilirubin), and Other (Total Protein, CK, Uric Acid, and LD panel)
 - Coagulation and thrombosis screens (PT, PTT, D-dimer)
 - Thyroid function tests
 - Viral serologies for hepatitis A, B, C, HIV, HSV, EBV and CMV
 - EBV and CMV PCR
 - PPD (at risk subjects only, based on history or geography)
 - Folate level
 - B12 level
 - Iron panel (ferritin, transferrin, % saturation)
 - HLA typing (if not already available)
 - Pregnancy test (urine or blood HCG in women of child bearing potential)
 - Bone marrow aspiration and core biopsy, to be stained for standard morphologic analysis and quantitation of cellularity with hematoxylin and eosin, and special stains to assess reticulin and collagen, primitive stem and progenitor cells via CD34 immunohistochemistry, and other lineage-specific or special stains as indicated to classify any abnormalities.
 - Bone marrow chromosomal analysis via standard cytogenetic techniques
 - Telomere length of leukocytes
 - Flow cytometry of the peripheral blood to quantitate GPI-negative cells
 - Lymphocyte peripheral blood phenotyping (analysis of T, B, and NK subsets via flow cytometry)
 - Chest X-ray- this does not need to be performed if a clinically indicated chest CT is performed to reduce the radiation burden

- EKG
- Placement of a central line if subject does not have a pre-existing indwelling central venous catheter

6.2 On Study Monitoring, Day 1 of h-ATG Through Hospital Discharge

On treatment monitoring will consist of the following, unless the hospitalization is interrupted due to the participant leaving the hospital “on pass” but not to exceed more than 7 days:

- Pregnancy test (urine or blood HCG in women of child bearing potential) does not need to be repeated if done within two weeks (Day 0 to Day -14)
- CBC with differential (daily)
- Acute care, Mineral, Hepatic and Other panel (every other day)
- Reticulocyte count (weekly +/- 3 days)
- Vital signs (daily)
- CsA blood level will be monitored every week (+/- 3 days) while inpatient in the hospital and continued per section 6.3. The blood level will be monitored to ensure therapeutic range of 200 – 400 ng/ml is achieved. CsA dosage will be adjusted to target this range. More frequent drug serum levels may be obtained as needed to achieve target therapeutic levels and avoid toxicity.

6.3 On Study Monitoring (hospital discharge through 6 months)

After completing h-ATG administration, subjects will remain hospitalized until clinically stable. Post-discharge, subjects may be followed by their home physician or at the Clinical Center. Progress notes and laboratory results from home physicians will be faxed to the research nurse. Standard of care tests will be done as needed and may include the tests listed below. Changes in frequency of the tests below will be performed as clinically indicated at the investigators discretion.

- Complete blood counts with differential every 1-2 weeks. Only the following parameters will be recorded in the clinical database because of their relevance to the underlying disease and study treatment: absolute neutrophil count (ANC), or neutrophil percentage and white blood cell count if an absolute neutrophil count is not provided, hemoglobin, platelets, and absolute reticulocyte count (or reticulocyte percentage and red blood cells [RBC] if an absolute reticulocyte count is not provided).
- Chemistry panel (NIH Acute care, Mineral, Hepatic and Other panel, home laboratory chemistry panel must include electrolytes, hepatic transaminases, urea nitrogen (BUN), serum creatinine, and total bilirubin). Only the following parameters will be recorded in the clinical database because of their relevance to the underlying disease and study treatment: aspartate aminotransferase (AST), alanine aminotransferase (ALT), alkaline phosphatase (ALP), total and direct bilirubin, creatinine, blood urea nitrogen (BUN), glucose, sodium, potassium, CO₂ and chloride.
- CsA blood level will be monitored every week for the first month and then every other week for the remainder of the treatment period once levels are stabilized in the therapeutic range of 200 – 400 ng/ml. CsA dosage will be adjusted to target this range unless participants cannot tolerate therapeutic dosing of CsA. More frequent drug serum levels may be obtained as needed to achieve target therapeutic levels and avoid toxicity, and conversely less frequent levels may be obtained as needed in individuals unable to tolerate therapeutic dosing of CsA. The dose may not necessarily be adjusted following every out of range CsA level, rather the decision to adjust the dose will be determined by the clinician judgement based on multiple data sources, that could include but not limited to time of measurement, prior trend of CsA levels, estimation of steady state, concomitant medications that may affect CsA metabolism, and renal function. CsA monitoring will be discontinued at 6 months for all cohorts
- HRQL survey administration (pre-eltrombopag; within 2 days of day 14 post ATG on cohorts 1 and 2)

(Surveys will not be required for the Extension and Exploratory Laboratory Cohort.)

Landmark 3-month and 6-month monitoring

Subjects must be evaluated at the NIH Clinical Center at the 3- and 6-month (+/-10 days) time points

- History and physical examination
- Complete blood counts with differential
- Acute care, Mineral, Hepatic and Other-panel
- Reticulocyte count
- Urine pregnancy test (woman of childbearing age only)
- Bone marrow aspiration and core biopsy, to be stained for standard morphologic analysis and quantitation of cellularity with hematoxylin and eosin, and special stains to assess reticulin and collagen, primitive stem and progenitor cells via CD34 immunohistochemistry, and other lineage-specific or special stains as indicated to classify any abnormalities
- Bone marrow chromosomal analysis via standard cytogenetic techniques
- Flow cytometry of the peripheral blood to quantitate GPI-negative cells
- Lymphocyte peripheral blood phenotyping (analysis of T, B, and NK subsets via flow cytometry)
- Peripheral blood for pharmacokinetic sampling (3-month, cohort 1; also, samples may be drawn any day between day 8 through day 30 on the extension cohort starting with subject #120). Pharmacokinetic sampling will not be collected for Exploratory Laboratory Cohort.
- HRQL survey administration (Surveys will not be required for the Extension and Exploratory Laboratory Cohort.)
- EKG (required at month 3 visit, may be performed at other time points)

